## **5.8 Interim Analysis**

There will be no interim analyses for efficacy or futility for this trial.

## **5.9 Demographic and Baseline Characteristics**

Demographic and baseline characteristics will be summarized for all participants. Caregiver characteristics to be examined may include, age, gender, race/ethnicity, spirituality, employment, education (years), co-morbidities, caregiving (years), household members. Patient characteristics to be examined may include: age, gender, race/ethnicity, Karnofsky performance status, HCT-Comorbidity Index, primary disease, disease risk group, number of treatments received before transplant, conditioning regimen, donor type, donor source, degree of match.

## **5.10 Analysis Populations and General Analysis Guidelines**

### **5.10.1 Primary Analysis Population**

All participants enrolled, consented, and completing at least the baseline outcome measures will be included in the primary analysis population. Analyses for the primary and secondary endpoints will use the primary analysis population: Caregivers of adult patients [age  $\geq 18$  years] will be analyzed separately from caregivers of pediatric patients [age 5-17 years]). The primary analysis will occur once all patients have been followed for 120-days post-transplant, data adjudication completed, and data are locked.

### **5.10.2 General Analysis Guidelines**

Primary analyses for the primary, secondary, and exploratory endpoints will use the primary analysis population. Analyses of each endpoint in each population will follow the analysis plans, as described below. We expect minimal missing data ( $<5\%$ ) for the primary endpoint and secondary endpoints based on past experience with Roadmap 1.0 studies.

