- 3.2.13 Health care utilization data. Patient health care utilization data (e.g., total count of hospital days, emergency department visits, readmissions, and ambulatory care clinic visits) will be captured through the electronic health record as well as self-report (i.e., if the patient is re-admitted at an outside hospital other than a participating site). Caregiver health care utilization data (e.g., hospital admissions, emergency department visits, and ambulatory care clinic visits) will be collected through self-report at the day 30 (+/-14) and day 120 (+/- 30) post-HCT PRO assessment period. The study team may access the electronic medical records for 1 year from the date of study enrollment.
- 3.2.14 Mobile Application Rating Scale (MARS) was added to the day 120 questionnaire to obtain user experience of the Roadmap 2.0 app.
- 3.2.15 Social Rhythms Application. We are interested in looking at how circadian rhythm may affect the participant's overall health. Participants may upload retroactive data from the Fitbit and will receive a personalized report about their circadian rhythm. Participant will be encouraged to upload their data at baseline (+/- 14 days), day 30 (+/- 14 days), and day 120 (+/- 30 days).

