#### **4.8 Post-Intervention Evaluation**

PROMIS Patient-Reported Outcomes (PROs) Well-being or HRQOL assessments will be obtained at days 30 (+/- 14) and 120 (+/- 30) post-HCT, during and at the end of the intervention period, respectively. The surveys will be obtained through Qualtrics, which will be linked directly to the Roadmap 2.0 app on the mobile phone. Based on prior work, our Study Team has experience administering PROMIS PROs on mobile devices. If a participant relapses, our team will continue to collect clinical data post-transplant. In the event of a relapse, the patient will be censored, and we will not collect any further surveys from the patient or caregiver.

Missing surveys will not be considered a protocol deviation.

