## **5.11 Analysis of Primary Endpoint**

Analysis will be an intent-to-treat analysis that includes all caregivers. Mean Global Health scores for each arm at day 120 will be compared using a two-sample *t*-test (or Wilcoxon Rank Sum test if non-normality is apparent) with a significance level of 0.05. Linear regression models will be performed to complement the results of the *t*-test and adjust for specific baseline caregiver characteristics (e.g., demographic, social, environmental) to increase the precision of our inference. We plan to do analyses separately for allo dyads, auto dyads, and pediatric dyads, although we have only powered the study for the analysis in the allo dyads. There is a possibility that patient characteristics will be unbalanced since our randomization scheme will be applied to caregivers. Thus, our models also will assess potential moderating or mediating effects, described below.

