### **5.13.3 Caregiver and patient overall survival**

Death from any cause will be calculated from randomization to death or loss to follow-up. Participants alive at last follow-up will be censored. Survival curves will be calculated for each arm using the methods of Kaplan and Meier and will be compared between arms using the log-rank test.

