## APPENDIX D: CAREGIVER- AND PATIENT-REPORTED OUTCOME MEASURES

### NIH PROMIS Tools

SELF-REPORT				
	Adult Patient (age ≥ 18 years)	Pediatric Patient (ages 8-17 years)	Adult Caregiver (≥ 18 years)	Parent Proxy for Pediatric Patients (ages 5- 17 years)
Baseline Caregiver Assessment			44	
Global Health	10	9	10	9
Companionship	4		4	
Self-Efficacy for Managing Symptoms	4		4	
Self-Efficacy for Managing Daily Activities	4		4	
Positive Affect and Well-Being	9	10 (ages 13-17 years)	9	
Emotional Support	8	7	8	
Sleep Disturbance		4		4
Caregiver Anxiety			6	
Caregiver Strain			6	
Perceived Stress Scale	10		10	
Profile 25* and 29+2†	29	25	29	25

\*A collection of 4-item short forms assessing anxiety, depressive symptoms, fatigue, pain interference, physical function-mobile, and peer relationships as well as a single pain intensity item.

†A collection of 4-item short forms assessing anxiety, depression, fatigue, pain interference, physical function, sleep disturbance, and ability to participate in social roles and activities as well as a single pain intensity item.

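### The baseline-completion condition is extended to survival, sensor and record-based endpoints that need no questionnaire, and the plan's statements on its reach conflict

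*Combined protocol and SAP*

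**What the plan says.** Section 5.10.1 defines a single population: "All participants enrolled, consented, and completing at least the baseline outcome measures will be included in the primary analysis population". On where it applies, the same section says: "Analyses for the primary and secondary endpoints will use the primary analysis population". Section 5.10.2 goes further: "Primary analyses for the primary, secondary, and exploratory endpoints will use the primary analysis population". For the primary endpoint, section 5.11 says something different again: "Analysis will be an intent-to-treat analysis that includes all caregivers".

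Three exploratory analyses do not depend on a baseline questionnaire, and none names its own population:

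- **Survival (5.13.3).** "Death from any cause will be calculated from randomization to death or loss to follow-up".
- **Activity and sleep (3.2.12, 5.13.5).** These are recorded continuously by the wearable sensor.
- **Patient utilization (3.2.13, 5.13.6).** Patient counts "will be captured through the electronic health record as well as self-report". Caregiver utilization differs: 3.2.13 collects it by self-report at days 30 and 120.

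On timing, section 4.7 asks only that baseline assessments come before the intervention. Section 5.5 states that the arms are not blinded.

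**The concern.** A condition suited to questionnaire scores has been carried over to endpoints observed by other means. A patient can be randomized, have a known vital status, a complete health record and a stream of Fitbit data, and still be excluded from all three comparisons because baseline measures are missing. Section 5.13.3 starts the survival clock at randomization, so the natural population for that curve is everyone randomized.

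Two things are at stake. The first is whether these comparisons remain as-randomized, which depends on whether baseline completion can occur after the arm is known. The second is pre-specification. With 5.10.1, 5.10.2 and 5.11 pointing in different directions, an analyst cannot tell who enters the survival curve, and the choice could be made after the data are seen.

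**Working it through.** **Step 1: which population governs each analysis.**

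- Primary endpoint: 5.10.1 and 5.10.2 impose the baseline condition; 5.11 says intent-to-treat for all caregivers. In conflict.
- Secondary endpoint: 5.10.1 and 5.10.2 agree on the baseline condition.
- Exploratory endpoints: 5.10.2 imposes the condition, 5.10.1 does not list them, and 5.13.3, 5.13.5 and 5.13.6 are silent. The only statement that covers them is 5.10.2, so the condition applies as written.

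**Step 2: does the endpoint need a baseline questionnaire?** Survival, no. Sensor activity and sleep, no. Patient utilization from the health record, no. Section 5.13.6 ties capture to the questionnaire assessments, but counts over the 120 days after transplant are follow-up data and do not depend on a baseline form.

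**Step 3: can completion follow randomization?**

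- Section 4.7 fixes baseline only relative to the intervention.
- Section 2.5.1 schedules the training session for dyads already randomized.
- Section 4.6 allows caregiver demographic data within 30 days of randomization, without saying on which side.
- Against this, the app that links to the surveys is downloaded at consent (4.3, 4.7), and the Time and Events Table puts questionnaires before admission.

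Both orders are therefore possible.

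**Step 4: size.** The plan gives no figure for baseline non-completion, so there is none to reproduce. Inputs from the documents are 300 dyads (Accrual Objective) and 8% death before day 120 (5.7). The non-completion rate m is assumed. Section 5.7 lists the 8% in sizing 83 caregivers per arm (2 × 83 = 166, the allogeneic target), so applying it to all 300 patients is also an assumption, as is equal mortality in completers and non-completers.

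Expected deaths: 300 × 0.08 = 24. Patients lost: 300 × m. Deaths lost: 300 × m × 0.08.

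| m (assumed) | Patients lost | Deaths lost |
|---|---|---|
| 2% | 6 | 0.48 |
| 5% | 15 | 1.2 |
| 10% | 30 | 2.4 |

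Restricted to the 166 allogeneic patients, the expected deaths are 166 × 0.08 = 13.3. At m = 2% to 10%, 3.3 to 16.6 patients and 0.27 to 1.33 deaths are lost.

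**Step 5: effect on the trial's sizing.** None. Section 5.7 sizes the trial on caregiver HRQOL. With 67 per arm and a standardized difference of 0.5, the noncentrality is 0.5 × √(67/2) = 2.89 on 132 degrees of freedom. The two-sided 5% t-test then has power 0.82, consistent with the stated 0.80.

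**The case against.** The strongest reply is that the documents contain unreconciled text rather than one settled rule: 5.10.1 omits exploratory endpoints and 5.11 promises intent-to-treat. Section 5.10.2 also governs only primary analyses, so an all-randomized analysis is not forbidden. This stands, and it is why the point concerns reconciliation as well as exclusion. It does not remove the gap, because no such analysis is specified.

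Four stronger readings may tempt a reader. The documents do not support them.

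- **That non-completion at baseline is expected.** The sentence "Missing surveys will not be considered a protocol deviation" stands in section 4.8, which concerns days 30 and 120. Section 4.7, on baseline, has no counterpart. The 10% in 5.7 is for missing day-120 questionnaires, and the figure below 5% in 5.10.2 is for the primary and secondary endpoints.
- **That the sickest patients are the ones lost.** Nothing shows this, and the schedule puts the form before admission for transplant. If non-completers had three times the mortality of completers, deaths lost would be 300 × m × 3 × 0.08/(1 + 2m): 3.3 at m = 5% and 6.0 at m = 10%. The factor of three is an assumption with no source in the plan.
- **That children aged 5–7 can never qualify.** Appendix D starts patient self-report at age 8, but parent-proxy forms cover ages 5–17, and objective 2.3.2.4 treats the proxy as a pediatric measure. What is missing is a statement that proxy completion counts.
- **That the comparisons are certainly biased.** If baseline is completed before randomization, the exclusion rests on a pre-randomization characteristic and does not distort the comparison of arms.

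It is also fair to say that the affected endpoints are exploratory and unpowered, and that the argument does not extend to self-reported caregiver utilization.

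**Conclusion.** The point holds as a defect of scope and consistency. As written, 5.10.2 removes randomized patients without baseline measures from survival, sensor and patient record-based utilization comparisons that do not need those measures. At an assumed 2–10% non-completion, this is about 6–30 of 300 patients and, with 8% mortality applied throughout, about 0.5–2.4 of roughly 24 deaths. The true loss is unknown and could be negligible.

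The consequence depends on timing that the plan leaves open. After randomization in an unblinded trial, completion may be related to arm, and the comparison may not be as-randomized. Before randomization, the cost is precision and generalizability only. The primary sample size is untouched. Because the endpoints are exploratory, this should be corrected but does not threaten the main result. The conflict between the baseline condition and the intent-to-treat statement in 5.11 does bear on the primary endpoint and needs resolving in the same edit.

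**What to change.** Change the SAP wording as follows.

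1. In 5.10.2, remove the baseline-completion condition for survival (5.13.3), wearable activity and sleep (5.13.5) and patient utilization from the health record (5.13.6). State that these use all randomized participants with available data, by assigned arm, except data removed on withdrawal under 4.9.
2. Keep self-reported caregiver utilization separate, since it exists only where the day-30 or day-120 report was given.
3. Say how 5.13.6 handles patients who are randomized but never transplanted (5.7 allows 5%), because its window starts at transplant.
4. Reconcile 5.10.1 and 5.10.2 with the intent-to-treat statement in 5.11. Do not do this by confirming the baseline condition for the primary endpoint.
5. For questionnaire endpoints, state that parent-proxy completion counts as baseline for pediatric patients.

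The cost is a few sentences. No new data, staff or participants are needed, and the sample size does not change. The downside is small: the analysis sets will differ between questionnaire and non-questionnaire endpoints, so each table should state its denominator.

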## **5.11 Analysis of Primary Endpoint**

Analysis will be an intent-to-treat analysis that includes all caregivers. Mean Global Health scores for each arm at day 120 will be compared using a two-sample *t*-test (or Wilcoxon Rank Sum test if non-normality is apparent) with a significance level of 0.05. Linear regression models will be performed to complement the results of the *t*-test and adjust for specific baseline caregiver characteristics (e.g., demographic, social, environmental) to increase the precision of our inference. We plan to do analyses separately for allo dyads, auto dyads, and pediatric dyads, although we have only powered the study for the analysis in the allo dyads. There is a possibility that patient characteristics will be unbalanced since our randomization scheme will be applied to caregivers. Thus, our models also will assess potential moderating or mediating effects, described below.

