#### **3.2 Exploratory Endpoints**

- 3.2.1 Caregiver HRQOL will be assessed by the PROMIS Global Health and Profile 29+2 scales at baseline (pre-intervention) and days 30 post-HCT.
- 3.2.2 Caregiver and patient HRQOL will be assessed by the PROMIS Companionship scale at baseline (pre-intervention), and days 30 and 120 post-HCT.
- 3.2.3 Caregiver and patient HRQOL will be assessed by the PROMIS Self-Efficacy for Managing Symptoms and Self-Efficacy for Managing Daily Activities scales at baseline (pre-intervention), and days 30 and 120 post-HCT.
- 3.2.4 Caregiver and patient HRQOL will be assessed by the PROMIS Positive Affect and Well-Being scale at baseline (pre-intervention), and days 30 and 120 post-HCT.
- 3.2.5 Caregiver and patient HRQOL will be assessed by the PROMIS Emotional Support at baseline (pre-intervention), and days 30 and 120 post-HCT.

- 3.2.6 Caregiver and patient HRQOL will be assessed by the Perceived Stress Scale at baseline (pre-intervention), and days 30 and 120 post-HCT.
- 3.2.7 Caregiver and patient HRQOL will be assessed by the Resilience, Optimism and Gratitude scales at baseline (pre-intervention), and days 30 and day 120 post-HCT.
- 3.2.8 Patient HRQOL will be assessed by the PROMIS Sleep Disturbance scale at baseline (pre-intervention), and days 30 and 120 post-HCT.
- 3.2.9 Caregiver and patient negative and positive dyadic interaction will be assessed by measures of the Dyadic Relationship Scale at baseline (pre-intervention), and days 30 and 120 post-HCT.
- 3.2.10 Caregiver HRQOL will be assessed by the TBI-CareQOL (PROMIS affiliate) Caregiver Anxiety at baseline (pre-intervention), and days 30 and 120 post-HCT.
- 3.2.11 Caregiver HRQOL will be assessed by the TBI-CareQOL (PROMIS affiliate) Caregiver Strain scale.
- 3.2.12 Activity data. Caregiver and patient activity (steps) and sleep will be measured continuously from the start to the end of the intervention (day 120 post-HCT) through wearable sensors.

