## **5.7 Sample Size Considerations**

The power calculation was completed by [name] using simulations in the statistical package R. Our primary endpoint (i.e., caregiver health-related quality of life from the PROMIS® Global Health scale) is focused solely on this outcome in caregivers, while our secondary endpoints are based on outcomes for both caregivers and patients. Given this, we determined our sample size based solely on caregivers. The age- and sex-adjusted norm for the Global Health scale is 50 points, with a standard deviation of 10 points. These statistics have been shown to be generalizable to the allogeneic BMT population. Our study will have power of 0.80, assuming a two-sided Type I error rate of 0.05, to detect an effect size of 0.5 between the intervention and control arms if 67 caregivers are enrolled in each arm. A mean difference of one-half a standard deviation is biologically meaningful

and is considered a medium effect size for clinical trials. We will accrue a total of 83 caregivers in each arm to account for dropout, assuming a 5% failure to undergo BMT, 8% death before day 120, and 10% missing day 120 PRO from participants. These percentages are inflated but based on adjustments of published BMT data.

Because our main goal is to assess the primary objective in adult allo dyads, we plan accrue approximately 260 dyads with adult patients, as that is the expected number of total adult dyads needed to enroll at least 166 allo dyads. We also plan to enroll approximately 40 dyads with pediatric patients in the time it takes to enroll the 260 adult dyads.

PROMIS® measures use Item Response Theory (IRT), a family of statistical models that link individual questions to a presumed underlying trait or concept of global health represented by all items in the scale. PROMIS® instruments are scored using item-level calibrations. The most accurate way to score a PROMIS® instrument is to use the HealthMeasures Scoring Service, which our Study Team has experience with ([name], Co-I and [name], Co-I). This method of scoring uses “response pattern scoring,” which uses responses to each item for each participant. Response pattern scoring is especially useful when there is missing data (i.e., a respondent skipped an item), or different groups of participants responded to different items).

There are four key features of the score for PROMIS® Global Health:

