### **5.13.2 Caregiver and patient PROs (see Appendix C)**

All questionnaires will be scored according to coding manuals. The resulting scores will be compared between arms at baseline and days 30 and 120 using the Wilcoxon Rank Sum test. Outcome measures will be compared between arms using linear regression modeling of day 30 and day 120 outcomes after adjusting for baseline scores. We also will model the outcomes from all three time points simultaneously using a linear mixed model to account for within-subject correlation, as well as adjust for possible moderating or mediating characteristics of the caregiver or patient.

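### The primary test leaves out the baseline Global Health score, which the plan already collects and requires, and so gives up power that a baseline-adjusted analysis would keep

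*Combined protocol and SAP*

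**What the plan says.** Section 5.11: "Mean Global Health scores for each arm at day 120 will be compared using a two-sample" *t*-test at the 0.05 level, with a Wilcoxon rank sum test to be used instead if non-normality appears. Linear regression is planned as a complement, to "adjust for specific baseline caregiver characteristics (e.g., demographic, social, environmental) to increase the precision of our inference". The baseline Global Health score is not named among those characteristics.

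Section 3.2.1: "Caregiver HRQOL will be assessed by the PROMIS Global Health and Profile 29+2 scales at baseline (pre-intervention) and days 30 post-HCT". Section 5.10.1 admits to the primary analysis population only participants who completed at least the baseline outcome measures.

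Section 5.13.2, under exploratory endpoints: "Outcome measures will be compared between arms using linear regression modeling of day 30 and day 120 outcomes after adjusting for baseline scores". The same section plans a linear mixed model over all three time points, which may also adjust for moderating or mediating characteristics.

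Section 5.7: "Our study will have power of 0.80, assuming a two-sided Type I error rate of 0.05". The target there is a difference of half a standard deviation, and the number given for it is 67 per arm. It also states: "The age- and sex-adjusted norm for the Global Health scale is 50 points, with a standard deviation of 10 points". It gives no correlation between baseline and day-120 scores and takes no credit for adjustment.

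**The concern.** The plan gives precision as the reason for adjusting, then leaves the confirmatory test unadjusted. The covariate most directly related to the endpoint, the same scale in the same caregiver before the intervention, is adjusted for only in exploratory work. If baseline and day-120 scores are materially correlated, the exploratory estimate will be more precise than the primary one, and the primary test will run at lower power than the collected data allow.

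The margin is thin, because the design expects to finish close to 80% power after losses. The choice between *t*-test and Wilcoxon is also left to a judgement made on the data. Section 5.11 gives no criterion for it, and section 5.5 says the statistician is not blinded.

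**Working it through.** **Inputs.** From 5.7: two-sided alpha 0.05, effect 0.5 SD (5 points on an SD of 10), 67 evaluable per arm for power 0.80, 83 accrued per arm, and losses of 5%, 8% and 10%. From 5.4: 1:1 allocation. The correlation r is not in the documents, so values from 0 to 0.7 are an assumption.

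**Step 1: reproduce the plan's figure.** For a two-sample *t*-test with n per arm, the noncentrality is d·√(n/2) on 2n − 2 degrees of freedom.
- The smallest n for 80% power at d = 0.5 is 64 (63 by the normal approximation).
- At n = 67 the noncentrality is 0.5·√33.5 = 2.894 and power is 0.819.
- With the Wilcoxon asymptotic efficiency of 3/π, the required n is 64/0.955 = 67.0, and power at 67 is 0.801.

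The stated 0.80 at 67 per arm is therefore supported. It matches the Wilcoxon variant closely.

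**Step 2: evaluable number under the plan's own losses.** Adding the losses gives 83 × (1 − 0.23) = 63.9. Compounding them gives 83 × 0.95 × 0.92 × 0.90 = 65.3. I use 65 per arm.

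**Step 3: adjust for baseline.** ANCOVA on baseline reduces the residual SD from 10 to 10·√(1 − r²). The standardised effect becomes 0.5/√(1 − r²), on 2n − 3 = 127 degrees of freedom. The unadjusted sample with the same precision is 65/(1 − r²) per arm.

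| Assumed r | 1 − r² | Power, 65 per arm | Equivalent unadjusted n per arm |
|---|---|---|---|
| unadjusted | – | 0.81 | 65 |
| 0 | 1.00 | 0.81 | 65 |
| 0.2 | 0.96 | 0.82 | 67.7 |
| 0.3 | 0.91 | 0.84 | 71.4 |
| 0.4 | 0.84 | 0.87 | 77.4 |
| 0.5 | 0.75 | 0.90 | 86.7 |
| 0.6 | 0.64 | 0.94 | 101.6 |
| 0.7 | 0.51 | 0.98 | 127.5 |

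The row at r = 0 shows that adjusting costs essentially nothing even if baseline predicts nothing.

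**Step 4: check by simulation.** With 67 per arm and 20,000 runs, the *t*-test and ANCOVA rejected in 0.823 and 0.911 of runs at r = 0.5, and in 0.822 and 0.949 at r = 0.6. The formula gives 0.913 and 0.949 for ANCOVA at 67 per arm.

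**The case against.** The best case for the plan is that nothing here is an error. In a randomised trial the unadjusted comparison is valid and its standard error already allows for chance baseline imbalance. A reader might infer that the primary estimate is biased or the trial undersized for its stated test. The documents support neither: step 1 confirms the plan's target.

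The gain is also uncertain. Baseline falls in the peri-transplant period, which section 1.2 describes as one of marked distress. The outcome follows about four months later with a 30-day window either side (4.8). A low r is possible, and at r = 0.2 the gain is only 1.5 points of power (0.823 against 0.808). That the baseline score will be the strongest predictor is an expectation, not something the documents show.

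The plan is not without adjustment either. The covariate list in 5.11 is given by example, so the baseline score is unnamed but not excluded, and 5.13.2 will produce an adjusted estimate. What stands against this is that none of it binds the confirmatory test.

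Two further steps are tempting and should not be taken:
- **Promoting the 5.13.2 mixed model because it is already planned.** Section 3.1 makes caregivers of patients who relapse or die before day 120 non-evaluable, and 4.8 stops surveys after relapse. A mixed model using baseline and day-30 scores would bring these caregivers in under a missing-at-random assumption and change what is estimated. As worded, the model may also adjust for mediators, which can distort the treatment effect.
- **Quoting a lower power after relapse losses.** The allowance in 5.7 has no relapse term, so evaluable numbers could fall below 64 or 65. The documents give no relapse rate, so no figure can be derived.

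One condition is real. Baseline is defined only as before the intervention (3.2, 4.7), the arms are open (5.5), and patients who recently had a transplant may enrol (2.4.1.7). If caregivers answer the baseline survey knowing their arm, adjusting for it could introduce bias.

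**Conclusion.** The point holds as one of lost efficiency. The primary test is unadjusted although the baseline score is collected and is required for the primary population. At 65 evaluable per arm and an effect of 0.5 SD, the loss is about 1.5 points of power at r = 0.2, about 10 at r = 0.5 and about 17 at r = 0.7. These figures rest on the assumed r, on normal scores with equal SD in both arms, and on a baseline unaffected by allocation. They apply to ANCOVA, not to the mixed model, and to the adult allogeneic comparison for which 5.7 and 5.11 power the study.

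The open choice between *t*-test and Wilcoxon is a gap in specification. A reader might infer an inflated type I error, but none has been shown. The change is worth making, but the trial does not fail without it.

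**What to change.** Before outcome data are reviewed by arm, amend 5.11 as follows.

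1. Make the primary analysis an ANCOVA of the day-120 caregiver Global Health T-score on arm and baseline Global Health T-score, in the evaluable caregivers. Add transplant type, a stratification factor in 5.4, wherever strata are pooled. Report the arm difference with its 95% CI.
2. Keep the two-sample *t*-test and the Wilcoxon test as sensitivity analyses, and delete the data-dependent switch between them.
3. State in 4.7 that the baseline survey is completed before the arm is disclosed, and verify this from survey and allocation timestamps.
4. Keep the three-time-point mixed model of 5.13.2 as supportive.

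The cost is SAP and protocol wording plus the timing check. No extra data or participants are needed, and because 5.10.1 already requires the baseline measures, adjustment should exclude no one from the primary population. If some baseline surveys prove to have been completed after disclosure, the sponsor will need a stated rule for those caregivers, and the unadjusted sensitivity analysis then carries more weight.
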